3.4 Study Setting

To minimise risk of COVID-19 infection to participants, the research/clinical teams will follow local Trust policy and procedures based on the current UK government guidance.

The Exeter neonatal genetics testing service is part of the clinical team responsible for diagnosing NDM, EET1D and monogenic autoimmunity in the UK and internationally. We will identify people with EET1D, and NDM controls, for this research by the clinical diagnostic tests performed as part of this service.

Patients in the UK will be given information about the EET1D study by the Exeter/local clinical team liaising with them (this will give patients the chance to accept or decline contact about the research study). If willing to be contacted, a trained member of the EET1D/local study team will contact patients initially by phone, and arrange a visit in person at their local care provider (timed with a clinical visit where possible to minimise patient burden). All study information is available to clinicians and patients on our study website (<https://www.diabetesgenes.org/current-research/exe-t1d/>).

UK participants will be recruited under UK wide ethics. As an international referral centre, Exeter will recruit patients from international centres in collaboration with local clinicians that have specific Institutional Review Board (IRB) approval.

We have developed the protocol for recruitment of paediatric non-diabetic controls with collaboration from the Children's Surgical Services Directorate and R&D Department at Guy's and St Thomas' NHS Foundation Trust and affiliate of King's College London.

The *Exeter Clinical Laboratories* encompass the Exeter Blood Sciences Laboratory and Exeter Molecular Genetics Laboratory at the Royal Devon University Healthcare NHS Foundation Trust and will perform C-peptide, islet autoantibody and genetic tests.

Peripheral lymphocyte (PBMC) analysis for autoreactive CD4 and CD8 T cells will be performed by [name] (Leiden University Medical Center, Netherlands) and [name] (King's College London).

RNAseq will be performed by the Exeter team and by [name] at the Benaroya Research Institute, Seattle (USA).

Sites outside the UK will need to confirm the following capabilities in order to deliver the study:

- IRB approval (Study CI and Project Manager can offer support with the application).
- Sufficient staff time to undertake the recruitment, consent, sample and data collection, documentation and arrangements for sample transfer to Exeter, data entry, and all follow-up procedures, as detailed in the study design, for the full duration of their participants' involvement in the study.
- Ability to despatch blood samples on day of collection (or following day latest) to the Exeter Clinical Laboratories at the lead site in Exeter, UK.

NOTE:

- Samples transferred to the Royal Devon and Exeter Hospital Central Laboratories for analysis will be labelled with participant identifiable data (name, date of birth & NHS//CHI/hospital number) in accordance with the requirements for clinical sample analysis. Once initial analysis is complete, remaining samples will be anonymised and assigned an individual study code prior to storage that links to the participant's study ID. Consent to store samples will be sought; samples without consent to store will be destroyed.
- Consent status, data collected and local test results will be entered on the online database within 7 working days of the study visit.
- Full contact details for both participants and clinicians will be included in the information transferred to the lead site, to facilitate feedback of visit results. C-Peptide and antibody results will be provided to the Site PI within 10 days of sample receipt at Exeter. T1D-GRS and genetic results will be advised to the Site PI within approximately 8 weeks of sample receipt if patients meet criteria for genetic testing (ie diagnosed before 9 months). T1D GRS results will be reported following batched analysis.

4. Subject Selection

4.1 Number of Subjects and Subject Selection

Please refer to the Study Summary Flow Charts (pages 10-11).

Study 1: Study of existing patients with EET1D (n=100-130 v 100)

Study 2: Study of patients newly diagnosed with diabetes <24 mths (n=40-60 EET1D v 10-40 Monogenic / NDM controls)

Non-diabetic controls: As comparators, healthy non-diabetic patients, aged 0-6 y, undergoing elective surgery (n=60-80)

The Exeter Molecular Genetics Laboratory has been referred >3500 patients diagnosed <12 months from 84 countries and we currently receive ~200 referrals per year. This is the largest cohort in the world of babies diagnosed with diabetes in the first year of life.

40% of patients already identified are based in the UK. The remainder are located at international centres (n=30 centres) that have referred patients as part of clinical care. We will initially recruit within the UK and target people who have been diagnosed with diabetes and referred to the Exeter Molecular Genetics Laboratory already. We have already identified EET1D patients and their clinicians who are willing to take part in the study and are establishing the infrastructure to recruit

and study these people. The majority of patients already identified are diagnosed under the age of 6 months, but we will recruit patients with an age of diagnosis up to 24 months. We will also recruit eligible patients referred directly to [name] or who contact us upon learning of the study and will arrange for genetic testing where this has not been performed. A cohort of non-diabetic children will be recruited as controls at specified participating hospitals when attending elective surgery (eg hernia repair), with samples being collected after anaesthetic induction to minimise patient discomfort and burden.

During the first year of the study, recruitment from UK referrals was slower than anticipated and subsequently the COVID-19 pandemic has affected recruitment rates, so we will allow alternative referral methods and recruitment approaches:

- i) attempt to recruit patients from distant sites with multiple cases.
- ii) We have now thoroughly reviewed patients already referred to the Exeter team and anticipate fewer newly recruited patients from this cohort than originally predicted (e.g. due to death or out of date contact details). We have been approached by eligible patients directly and, with new referrals from clinicians, these may make up for this shortfall, so alternative referral methods will be permitted. Additionally, the rarity of this condition means predictions of recruitment are very difficult, as are power calculations for the proposed analyses. We plan to recruit as per this updated protocol (and the new recruitment routes) and then may propose revised recruitment targets in 12 months based on these altered recruitment strategies.
- iii) attempt to recruit healthy non-diabetic children as controls for Studies 1 and 2. Option 1 is to recruit healthy children when attending elective surgery at specified participating sites, as described above. As a second option, if recruitment proves slower than anticipated, we would recruit children with congenital non-immune thyroid disease when they attend paediatric clinic for blood draw (~5 times in the first year of their life), giving an opportunity for a sample to be collected for functional immune analysis. The recruitment priority will be children aged under 2 years but eligibility will be 0 to age 6 years.

Patients for study and controls (Studies 1 and 2)

Defining patients as EET1D:

Patients will be selected on the basis of:

- i) diagnosis of diabetes <24 months (with continued primary focus on recruitment of those diagnosed <12months)
- ii) exclusion of mutation in all 23 monogenic non-autoimmune neonatal diabetes genes using targeted capture Next Generation Sequencing(NGS) if diagnosed <12 months (3)
- iii) T1D GRS within distribution of T1D reference population(10).
- iv) Diagnosis of monogenic type 1 diabetes defined as a mutation in a gene known to cause type 1 diabetes (e.g. *FOXP3* and *STAT3*) or a Down's syndrome (added with additional funding for recruitment and analysis from The Leona M. and Harry B. Helmsley Charitable Trust).

Study 1: existing cases of any age meeting above criteria.

Study 2: new cases referred to Exeter Genetics Service or [name] within 12 months of diagnosis, meeting above criteria, and aged <24 months.

Comparison groups:

Study 1: Older age onset T1D. To allow comparison with later onset T1D, we will select duration-matched patients from our T1D research cohort of patients diagnosed at 1-20 years of age. They will be defined as T1D by clinical diagnosis, age of diagnosis, and treatment with insulin from diagnosis.

Studies 1 & 2:

Age- and duration-matched controls with monogenic / NDM (neonatal diabetes). We will identify, from referrals to Exeter, age- and duration-matched controls with proven monogenic (non-autoimmune) neonatal diabetes. Eligible patients will include people with neonatal diabetes caused by mutations in the Kir6.2 and SUR1 genes(11).

Non-diabetic controls. We will identify healthy children <6 years of age undergoing elective surgery.

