3.2 Study Aim

The EXE-T1D study will take people with T1D diagnosed before the age of 24 months and compare them to people with T1D diagnosed at more typical ages (1-20 years), and people diagnosed with non-autoimmune diabetes at a similar very young age (children with neonatal diabetes [NDM]), and infants without diabetes matched for age.

EXE-T1D is an observational study organised into two sub-studies:

Phase 1 aims:

Study 1: Cross-sectional study of existing patients with EET1D:

Aim: To compare clinical features, beta cell loss (measured by serum/urine C-peptide), islet-specific autoantibodies, T1D risk genes and autoreactive CD8 T cells in people already known to have EET1D and already referred to Exeter for genetic testing or directly to [name], to those people with T1D diagnosed at older ages (age 1-20 years).

Study 2: Study of newly referred patients:

Aim: To assess immune function (by measuring autoantibodies, autoreactive CD8 T cells and RNAseq of immune genes) at diagnosis and longitudinally in people with newly diagnosed EET1D compared to newly diagnosed monogenic neonatal diabetes.

Phase 1 recruitment:

Total recruited = 163: 137 to study 1, including 18 with fingerprick samples, and 24 to study 2. Numbers were affected by the COVID-19 pandemic and follow-up of UK study 2 patients is ongoing.

Phase 2 recruitment:

Total recruited = 267. To reflect the most valuable samples to date, we recruited 23 more patients with EET1D (reflecting incidence and referral rate), 1 monogenic / NDM control, 60 non-diabetic controls (age 0-6 years) and 20 newly diagnosed T1D controls. We prioritised recruitment to Study 2 (age <2 years). These patients are extremely rare and numbers are dependent on incidence and referrals so the above numbers reflect referral rates.

It is important to overlap recruitment of cases and controls to reduce risk of batch effects in immune and RNA analysis.

Phase 3 extension aims:

We will prioritise recruitment to Study 2 (age <2 years) plus age-matched non-diabetic controls and monogenic / NDM controls when identified. These patients are extremely rare and numbers are dependent on incidence and referrals so achieving the proposed targets depends on referral rates.

Primary Objective

The primary objective of the study is to compare beta cell function and islet autoantibodies in EET1D to T1D, NDM and non-diabetic controls.

Secondary Objectives

The secondary objectives of the study are:

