4.2 Inclusion Criteria

Study 1:

EET1D

- Aged 0 to 70 years
- Clinical diagnosis of diabetes or autoimmunity <24 months (+ evidence of WHO diabetes criteria)

T1D Controls

- Age 0-70 years (matched to above)
- Clinical diagnosis of T1D (diagnosed age 2-20 years)
- Insulin treated from diagnosis.

Monogenic / NDM controls

- Diagnosis of diabetes <12 months
- Diagnosis of monogenic / NDM (confirmed by Exeter Molecular Genetics Laboratory).

Study 2:

EET1D

- Aged 0 to 24 months at recruitment
- Clinical diagnosis of diabetes <24 months (+ evidence of WHO diabetes criteria); recruited within 12 months of diagnosis.
- Negative genetic test for mutations causing non-autoimmune neonatal diabetes
- Type 1 diabetes genetic risk score >50th centile of T1D reference group, or monogenic cause of T1D (e.g. *STAT3* or *FOXP3* mutation)

NDM controls

- Diagnosis of diabetes <12 months
- Diagnosis of NDM (confirmed by Exeter Molecular Genetics Laboratory).

Non-diabetic controls for Studies 1 and 2:

- Aged 0-6 years (The recruitment priority will be children aged under 2 years but to include children aged 2-6 years)
- Attending specified participating hospital sites for elective surgery, including but not limited to: inguinal hernia repair, umbilical/midline hernia repair, orchidopexy, gastrostomy insertion/change, hypospadias repair, cleft palate repair, excision of accessory digit, laryngoscopy, adenoidectomy, tonsillectomy, MRI under general anaesthesia, eye surgery.

Should recruitment be slower than anticipated, we would recruit children with congenital non-immune thyroid disease when they attend paediatric clinic for blood draw.

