20.3 Appendix 3 – Study 2: Investigation of mechanisms of EET1D

In this second study, we will examine for mechanisms that can explain the very early onset of islet-specific autoimmunity in EET1D. This will involve looking for differences in genetics, maternal genetics, intra-uterine environment, and autoimmune function.

Genetic analysis

- i) **HLA high resolution sequencing:** we aim to define HLA to 6-digit definition by sequencing the entire 3.8Mb HLA region using a combination of CATCH-seq targeted capture with Pacific Biosciences sequencing in 100 patients with EET1D and 100 T1D patients (diagnosed 1-10 years) matched for 2 digit HLA genotype (DR3/DR4 haplotype combinations). The Pacific Biosciences technology provides an opportunity to fully interrogate the HLA region in these patients using long-read sequencing that avoids the difficulties of haplotyping with shorter read approaches(17). The Exeter group has extensive experience of analysing PacBio data (having been recently awarded a £1m MRC clinical infrastructure grant for the PacBio sequencing machine and associated computing). We will use the PacBio SMRT portal for analyses including de-multiplexing, generation of haplotypes, read alignment and variant calling. We will look for differences in frequencies of rare or novel risk variants between EET1D and T1D. For example, we will have 80% power to detect a rare variant that is present in 0.1% of controls, but >15% of cases at a $P<0.0005$.
- ii) **Maternal genetic factors: Non-inherited maternal allele (NIMA) and microchimerism analysis.**

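### Later-onset T1D comparators are diagnosed from age 1 in sections 3.2, 4.1 and Appendix 3 but from age 2 in section 4.2, so the first range overlaps the under-24-month case definition

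*Protocol*

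**What the plan says.** **Cases.** Section 4.1 selects EET1D patients on "diagnosis of diabetes <24 months (with continued primary focus on recruitment of those diagnosed <12months". The Study 1 criterion in 4.2 agrees: "Clinical diagnosis of diabetes or autoimmunity <24 months (+ evidence of WHO diabetes criteria". Section 4.1 adds further conditions. Neonatal diabetes genes must be excluded, but only if diagnosis was before 12 months. The T1D genetic risk score (GRS) must lie within the T1D reference distribution. A monogenic T1D or Down's syndrome diagnosis is also provided for.

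**Later-onset T1D comparators.** The lower age limit depends on the section:

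- 3.2, overall aim: "people with T1D diagnosed at more typical ages (1-20 years"
- 3.2, Study 1 aim: "to those people with T1D diagnosed at older ages (age 1-20 years"
- 4.1, comparison groups: "we will select duration-matched patients from our T1D research cohort of patients diagnosed at 1-20 years of age"
- 4.2, inclusion criteria for Study 1 T1D controls: "Clinical diagnosis of T1D (diagnosed age 2-20 years"
- Appendix 3, HLA sequencing: "100 T1D patients (diagnosed 1-10 years) matched for 2 digit HLA genotype"
- Appendix 3, microchimerism: T1D diagnosed at 1-10 years

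No text says which range prevails, and no rule assigns a person diagnosed at 12-24 months to one group.

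**The concern.** A comparator floor of 1 year would fit a case definition that stopped at 12 months. It does not fit one that runs to 24 months. The remaining case conditions do not reliably separate the groups in the overlap band: the neonatal gene exclusion is not required there, and a GRS within the T1D distribution is what an ordinary T1D patient would be expected to have.

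The EET1D v T1D contrast is part of the primary endpoint (C-peptide and autoantibodies). It also carries hypothesis (ii) and the older-onset comparison in hypothesis (iii). Any case-like people placed among the comparators would shrink these differences toward zero. The rare-variant comparison in Appendix 3 is the most exposed, because it relies on the variant being almost absent in controls.

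**Working it through.** **1. Overlap by section**

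| Source | Comparator age at diagnosis | Shared with cases (<24 months) |
|---|---|---|
| 3.2 (twice), 4.1 | 1-20 years | 12-24 months |
| Appendix 3, HLA and microchimerism | 1-10 years | 12-24 months |
| 4.2, Study 1 T1D controls | 2-20 years | none |

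Section 4.2 lists no T1D controls under Study 2, and Appendix 3, which describes Study 2, sets its own range. The 4.2 floor therefore does not clearly reach those two analyses.

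**2. Share of overlapping comparators, f**

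The protocol does not give f. The Background (1.1) equates diagnosis under 2 years with roughly the first centile, so f is about 1% in an unselected cohort. In the 1-10 year window the later diagnoses drop out. If s is the fraction of the cohort diagnosed at 1-10 years, f is about 1%/s. The protocol does not give s. As assumed examples only, s = 1/2 gives 2% and s = 1/3 gives about 3%.

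**3. HLA example (Appendix 3)**

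Inputs from the protocol: 100 v 100, P<0.0005, variant in 0.1% of controls and more than 15% of cases (15% used), stated power 80%. Method: two-sided Fisher exact test, power by full enumeration.

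With f = 0 the power is 80.8%, so the stated figure reproduces.

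With overlap, the control carriage rate is 0.001(1 − f) + 0.15·r·f, where r is carriage among overlapping comparators relative to cases (an assumption). At f = 1%:

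- r = 1: 0.00099 + 0.00150 = 0.00249
- r = 0.5: 0.00099 + 0.00075 = 0.00174

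| f | Power, r = 1 | Power, r = 0.5 |
|---|---|---|
| 0 | 80.8% | 80.8% |
| 1% | 76.6% | 78.7% |
| 2% (assumed) | 72.6% | 76.6% |
| 3% (assumed) | 68.7% | 74.6% |

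The sensitivity comes from the strict threshold. In the enumeration, no control carriers requires at least 12 case carriers for significance; a single control carrier raises that to 15.

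**4. Study 1 contrasts (12.3)**

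Inputs: 100 v 100, alpha 0.05, 50% v 30% or 0.6 SD. Normal approximation, two-sided. With fully case-like overlap, the comparator proportion is 0.30(1 − f) + 0.50f and the mean difference is 0.6(1 − f) SD.

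- f = 0: 82.8% and 98.9%
- f = 1%: comparator proportion 0.302, power 82.0%; difference 0.594 SD, power 98.7%

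The section states 90% for both contrasts, and neither figure reproduces under a two-sided test. That is a separate matter; the change from f = 0 to f = 1% is what counts here, and it is under one percentage point.

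**The case against.** The strongest reply is that 4.2 is the inclusion-criteria section and already separates the Study 1 groups: cases below 24 months, T1D controls from 2 years. The 1-year figures then look like text that was not updated. For Study 1 this largely stands. A reader might infer that the plan allows the same child to be case and control in the primary contrast. The documents do not support that, because it happens only if 4.2 is not applied. The reply does not cover Appendix 3, and 4.1 is itself the instruction for drawing comparators from the existing cohort.

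A reader might also infer that anyone diagnosed at 12-24 months fits both groups. Age alone is not enough under 4.1; the GRS or monogenic criterion must be met too.

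Nor do the documents support a large loss of power. The HLA example would fall to 61% or 46% only with f of 5% or 10% and carriage at the full case rate, and no passage gives such shares. Full-rate carriage is itself a worst case, since recruitment focuses on diagnosis before 12 months and most patients already identified were diagnosed before 6 months. The 15% is also the lower end of the stated effect: at 17%, power is still 88% with f = 1% and full carriage. Finally, 12.2 says the sample size was set for feasibility, not power.

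What remains is a contradiction in current text about who may be a comparator. That does not depend on f.

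**Conclusion.** The point holds as a correction that should be made, not as a fatal flaw. Sections 3.2, 4.1 and Appendix 3 permit T1D comparators from an age band that belongs to the cases; 4.2 does not. If 4.2 is enforced, Study 1 is protected. The HLA and microchimerism analyses are not.

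The direction of any bias is toward no difference, provided that overlapping patients are actually drawn and resemble cases. At the first-centile anchor of about 1%, the effect on the Study 1 contrasts is negligible, and the HLA example loses about 2 to 4 percentage points (from 81% to 79% or 77%). A larger loss needs a larger share. The 1-10 year window could raise it, by an amount the documents do not give.

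A reader might conclude that every EET1D v T1D result is diluted, or that misclassified comparators are already enrolled. The protocol shows neither: the share is unknown, and no text reports a comparator diagnosed before 24 months.

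**What to change.** - In 3.2 and 4.1, change the T1D comparator range to diagnosis at 2-20 years, matching 4.2. In Appendix 3, change it to 2-10 years for both HLA sequencing and microchimerism.
- Add one sentence stating that nobody is counted in both the EET1D and the T1D comparator group.
- Before the final batched analyses described in 5.3, check whether any T1D comparator was diagnosed before 24 months. If so, exclude that person from the comparator group, and count them as EET1D only if every case criterion is met.

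The cost is a wording amendment and a database query. The downside is the possible loss of a few comparators already matched on duration or HLA genotype, whose matches would then need review.

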4.2 Inclusion Criteria

Study 1:

EET1D

- Aged 0 to 70 years
- Clinical diagnosis of diabetes or autoimmunity <24 months (+ evidence of WHO diabetes criteria)

T1D Controls

- Age 0-70 years (matched to above)
- Clinical diagnosis of T1D (diagnosed age 2-20 years)
- Insulin treated from diagnosis.

Monogenic / NDM controls

- Diagnosis of diabetes <12 months
- Diagnosis of monogenic / NDM (confirmed by Exeter Molecular Genetics Laboratory).

Study 2:

EET1D

- Aged 0 to 24 months at recruitment
- Clinical diagnosis of diabetes <24 months (+ evidence of WHO diabetes criteria); recruited within 12 months of diagnosis.
- Negative genetic test for mutations causing non-autoimmune neonatal diabetes
- Type 1 diabetes genetic risk score >50th centile of T1D reference group, or monogenic cause of T1D (e.g. *STAT3* or *FOXP3* mutation)

NDM controls

- Diagnosis of diabetes <12 months
- Diagnosis of NDM (confirmed by Exeter Molecular Genetics Laboratory).

Non-diabetic controls for Studies 1 and 2:

- Aged 0-6 years (The recruitment priority will be children aged under 2 years but to include children aged 2-6 years)
- Attending specified participating hospital sites for elective surgery, including but not limited to: inguinal hernia repair, umbilical/midline hernia repair, orchidopexy, gastrostomy insertion/change, hypospadias repair, cleft palate repair, excision of accessory digit, laryngoscopy, adenoidectomy, tonsillectomy, MRI under general anaesthesia, eye surgery.

Should recruitment be slower than anticipated, we would recruit children with congenital non-immune thyroid disease when they attend paediatric clinic for blood draw.

